 - a. Group A patients will have sterile 2% lidocaine with Epinephrine 10 μ g/mL (Solution A1) soaked in surgical grade cotton applied to the donor site immediately after donor harvest until hemostasis is obtained according to the surgeon. If additional hemostasis is deemed necessary by the surgeon following use of 20cc (1 vial) of this Solution A1 then additional Epinephrine 10 μ g/mL will be used as per standard burn protocol. Following hemostasis, patients will have a sterile, nonpyrogenic solution of lidocaine 2% in isotonic saline (Solution A2) sprayed on the donor site of the grafted skin prior to emergence from general anesthesia. A maximum of 7mg/kg of lidocaine solution will be available for spraying. The site will then be covered with TheraBond dressing as per standard burn care used at our institution.
 - b. Group B (control group) patients will have sterile Epinephrine 10 μ g/mL solution (Solution B1) soaked in surgical grade cotton applied to the donor site immediately after donor harvest. A 20cc aliquot will be prepared in such a way as to be indistinguishable from Solution A1 by the OR team. If additional hemostasis is deemed necessary by the surgeon following use of 20cc (1 vial) of this Solution B1 then additional Epinephrine 10 μ g/mL will be used as per standard burn protocol. Following hemostasis, patients will have a control (placebo) sterile, nonpyrogenic solution of isotonic saline (Solution B2) sprayed over the donor site. The site will then be covered with TheraBond dressing as per standard burn care used at our institution.

- f) Assessment of the donor sites using the VNRS pain scores will be compared between groups in addition to the amount of narcotic pain medication required by these two groups. The amount of narcotic utilized will be analyzed per ideal body weight, per actual body weight in addition to donor site area.
- g) Lidocaine levels will be drawn at sixty minutes and six hours from application of study solution. These levels will be analyzed on a per patient and per graft size area basis to trend for systemic levels.
- h) Any adverse event occurring with the patient will be analyzed on a case-by-case basis. Wound infection rates of the donor sites at post op day 14-21 +/- 5 days will be compared between the two groups. Any adverse event deemed serious by the Principal Investigator will be submitted to the Institutional Review Board per institution policy.

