- b. Randomization procedures: Numerical randomization will be created using a computer generated numbers. Randomization envelopes will be created by research staff and maintained by the Investigational Drug Pharmacy. The Burn Study Team will alert the Investigational Drug Pharmacy to randomize each patient. The Investigational Drug Pharmacy will dispense the appropriate blinded solution for treatment. The Investigational Drug Pharmacy will dispense Lidocaine with Epinephrine or Epinephrine alone in blinded fashion for the donor site soaks. A 20cc bottle of Lidocaine with Epinephrine or Epinephrine alone will be emptied into a sterile unlabeled container prior to application of sprayed study treatment. The surgeon and OR team will remain blinded for this portion of the study. If additional hemostasis is required beyond the first study soak treatment; then the standard of care epinephrine soak will be utilized. The Investigational Drug Pharmacy will also dispense the randomized spray study treatment in an assembled applicator (LMA MADgic™) purchased for this project only. No unblinding identifiers will be on either applicators. The investigator will be blinded to all groups. Study Intervention:
 - i. Group A (Lidocaine Treatment Group): Graft site hemostasis will be obtained with 2% lidocaine and epinephrine 10 μ g/mL solution in normal saline soaked in surgical grade cotton gauze and placed over donor site for time determined by surgeon. Following hemostasis, 7mg/kg of 2% Lidocaine solution will then be sprayed on patient's donor site while under general anesthesia by burn surgeon in a sterile fashion. Upon emergence and transfer to PACU patient will be asked to rate his/her pain according to the VNRS for both donor site and overall pain. The amount of narcotics required in PACU and first 24 hours on floor will be documented. Rate of increase of narcotic requirement within the first 24 hours will also be analyzed. VNRS scores will be obtained immediately post operatively on arrival to PACU and in 24 hours.

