 - ii. Group B(Placebo Group): Graft site hemostasis will be obtained with a epinephrine 10 μ g/mL solution in normal saline soaked in surgical grade cotton gauze and placed over donor site for time determined by surgeon. Following hemostasis a control solution will be sprayed on patient's donor site while under general anesthesia by burn surgeon in a sterile fashion. Upon emergence and transfer to PACU patient will be asked to rate his/her pain according to the VNRS for both donor site and overall pain. The amount of narcotics required in PACU and first 24 hours on floor will be documented. Rate of increase of narcotic requirement within the first 24 hours will also be

analyzed. VNRS scores will be obtained immediately post operatively on arrival to PACU, 6 hours post treatment during blood draw and in 24 hours for both donor site and overall pain.

Study Table of Events

Study Assessments	Baseline	Surgical Procedure	0-24 hours post op	24-48 hours post op	Follow up (14-21 days)*
Informed Consent	X				
Inclusion/Exclusion	X				
Demographic Data	X				
Medical History	X				
Physical Exam	X				
Randomization		X			
Treatment		X			
OR Data Collection		X			
VNRS Pain Assessment			X**	X**	
Self-Reported Pain Assessment			X	X	
Wound Healing Assessment					X
Photographs		X			X

Narcotic Medication Data Collection		X	X	X	
Adverse/SAE Assessment	X	X	X	X	X
Lidocaine Level			X***		

* (+/- 5 days)

**Performed at 30 minutes after extubation, 2 hours, 6 hours and 24 hours post-op for both donor site and overall pain

***Performed at 60(+/-30 minutes) minutes and 6 hours (+/-60 minutes) post op

Safety Monitoring Plan

- a. The likelihood of adverse events in this study is very small. Lidocaine spray doses will be calculated (7mg/kg based on ideal body weight) to ensure patient is receiving safe doses. A safety analysis performed on our first 15 patients proved safety. All lidocaine levels obtained demonstrated levels significantly lower than potentially toxic dosing. We believe there could be improved pain control if more appropriate (higher) lidocaine doses are utilized. The method suggested for hemostasis with lidocaine and epinephrine is standard of care at some institutions including our own. It is regularly used by the ENT service. In addition, one of the surgeons in our study has used this method in the past.
- b. Patients will be monitored with pulse oximetry overnight per standard of care.

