- c. All patients enrolled in the study will have risks and benefits thoroughly explained to them.
- d. Any adverse events will be well documented and thoroughly investigated. Seriousness of event will be assessed by the Principal Investigator. All events deemed serious will be submitted to the University of Florida Institutional Review Board in accordance with institutional policy.
- e. Dressing site will be evaluated daily per standard of care by the burn team until hospital discharge.
- f. After 10 additional evaluable patients, have been enrolled a second safety analysis will be performed; all investigators will be involved in data interpretation.

Analysis Plan

An independent groups t-test (Student's t-test) will be performed to compare the mean rating between the difference of the two reported pain scale ratings. Each patient will be used as his/her own control by comparing the amount of narcotics utilized prior to surgery. An alpha level of 0.05 and power of 0.8 will be used to address the difference in the two groups. Given the desired alpha the sample size was estimated by pre-determined tables for certain values, by Mead's resource equation. With an effect size (Cohen's d) of 0.8 it is estimated that 25 patients in each

group will be needed in order to show statistical significance. An interim analysis will be conducted at 10 patients in each group and significance will be analyzed.

The amount of hydromorphone utilized in the PACU immediately post op and within the first 24 hours will be compared between the two groups and trended within the same group. Once again, an independent groups t-test will be performed to compare the mean quantity of hydromorphone required between the two groups. An alpha level of 0.05 and power of 0.8 will be used to address the difference in the two groups.

7. Possible Discomforts and Risks:

The patient's regular medical care will not change because they are enrolled in this study.

Possible risks to you may include:

- The risks from skin grafting and donor site include those associated with any surgical procedure that involves general anesthesia. These include reactions to the anesthesia, medications, nausea, pain, problems breathing, excessive bleeding, and infection.

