Appendix A.

DATA COLLECTION POINTS

Age
Race
Sex
Height
Weight
BMI
Date of Injury/Wound
Mechanism of Injury/Wound
TBSA % Burned /Size of wound
Medical History
Physical Exam
Randomization
OR Procedure
OR Date
OR Incision Time
OR Extubation Time
OR Medication Data Collection
Donor Site Dimensions
Lidocaine levels at 60 minutes and 6 hours post op
Time of Study Treatment Soak Placement
Additional Epinephrine Soak Required
Time of Study Treatment Spray Placement
Time of Therabond Placement

Time of PACU/BICU Admission (Post-operatively)

PACU/BICU Post –op Narcotic Medication

Documentation of Verbal Numerical Rating Scale Pain Assessment (Time): 30 minutes after extubation, 2 hours, 6 hours and 24 hours post op obtained by research staff for both donor site and overall pain

Self- Reported Pain Assessment (Time): Collect from EPIC for first 24 hours

Wound Healing Assessment (14-21 days post op[+/-5days]) Performed per standard of care

Photographs (OR and 14-21 days post op[+/-5days])

Adverse/SA Event Assessment

Overall Narcotic Medication Data Collection from EPIC (0-72 hours post op)

[figure not shown]
Date of new onset infection of donor site

Antibiotics for donor site infection

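### The pain t-test is specified on a difference of two unnamed ratings, all scheduled ratings follow the lidocaine, and the wording conflicts with the direct group comparison described elsewhere

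*Combined protocol and SAP*

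**What the plan says.** The pain test is in the first paragraph of the Analysis Plan (section 6, Research Plan). An independent-groups t-test will "compare the mean rating between the difference of the two reported pain scale ratings". The sentence does not say which two ratings, on which scale or at which times. The next sentence reads "Each patient will be used as his/her own control by comparing the amount of narcotics utilized prior to surgery". The same paragraph gives alpha 0.05, power 0.8, Cohen's d of 0.8, 25 patients per group and an interim look at 10 per group.

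Other sections describe the comparison and the schedule as follows.

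- Study Design f): "Assessment of the donor sites using the VNRS pain scores will be compared between groups". Study Design c) likewise lists donor-site and overall VNRS among the quantities compared between the two groups. Neither item mentions a difference of ratings.
- Study Table of Events, VNRS footnote: "Performed at 30 minutes after extubation, 2 hours, 6 hours and 24 hours post-op for both donor site and overall pain". Neither pain row has a mark under Baseline or Surgical Procedure.
- Group A text (Study Procedures b.i): "VNRS scores will be obtained immediately post operatively on arrival to PACU and in 24 hours".
- Group B text (Study Procedures b.ii): "VNRS scores will be obtained immediately post operatively on arrival to PACU, 6 hours post treatment during blood draw and in 24 hours".
- The spray goes on the "donor site while under general anesthesia by burn surgeon in a sterile fashion", after the soak.
- Appendix A, chart pain scores: "Collect from EPIC for first 24 hours".

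**The concern.** An independent-groups t-test already supplies the contrast between arms. If the variable put into it is itself a difference of two ratings, the test asks whether that difference varies by arm, not whether lidocaine patients have less donor-site pain. A change score is useful when one of its two values precedes treatment. Here none does: soak and spray are applied under anesthesia, and the first scheduled VNRS comes after extubation.

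Two pairs fit the wording. One is PACU arrival and 24 hours, the only times named in both group descriptions. The other is donor-site and overall pain, which are both asked at each assessment. In the first pair, both values carry the treatment effect. In the second, any relief that also lowers overall pain is subtracted.

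This is the only pain comparison with a named test, and the sample size stands in its paragraph. Followed literally, the sentence could make an effective treatment look inert or worse than placebo. If it is not followed literally, eight scores per patient (four times, two scales) are available and nothing says which is tested.

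**Working it through.** **Inputs from the documents.** Alpha 0.05, power 0.80, d = 0.8, 25 per group, independent-groups t-test (Analysis Plan). Sidedness is not stated; two-sided is assumed.

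**Inputs assumed.** The documents give no VNRS standard deviation, within-patient correlation or time course of effect. Assumed: an effect of 0.8 SD at the early rating, equal SDs for the two ratings, and correlation ρ = 0.5 with a range of 0.3 to 0.7.

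**Step 1: the plan's own figure.** Normal approximation: n = 2(1.960 + 0.842)² / 0.8² = 24.5, so 25 per group, as stated. With the noncentral t (48 df, critical value 2.01, noncentrality 0.8 × √(25/2) = 2.83), power at 25 per group is 79%; 26 per group would give 81%. The stated size therefore fits a direct two-group comparison of a variable whose standardised effect is 0.8.

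**Step 2: later minus earlier rating.** Let the effect be −0.8 SD early and −0.8k SD late, where k is the share retained. The change differs between arms by 0.8(1 − k) SD, and the SD of a change is √(2(1 − ρ)). So

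d_change = 0.8(1 − k) / √(2(1 − ρ)).

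At ρ = 0.5 the denominator is 1. A positive value means pain rises more on lidocaine.

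| Share retained at 24 h (k) | d_change, ρ = 0.5 | Rejection rate, ρ = 0.5 | ρ = 0.3 to 0.7 |
|---|---|---|---|
| 100% | 0 | 5% | 5% |
| 75% | +0.20 | 11% | 9–15% |
| 50% | +0.40 | 28% | 22–43% |
| 0% | +0.80 | 79% | 65–95% |
| 150% (effect grows) | −0.40 | 28% | 22–43% |

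In the 50% and 0% rows the rejections point against lidocaine. In the last row the sign is right but the effect is diluted.

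**Step 3: donor-site minus overall rating.** If a share q of the donor-site relief also shows in overall pain, d = −0.8(1 − q) / √(2(1 − ρ)).

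| Share also in overall pain (q) | d, ρ = 0.5 | Power, ρ = 0.5 | ρ = 0.3 to 0.7 |
|---|---|---|---|
| 0 | −0.80 | 79% | 65–95% |
| 50% | −0.40 | 28% | 22–43% |
| 100% | 0 | 5% | 5% |

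The sign reverses only if overall pain falls more than donor-site pain (q above 1).

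**Step 4: direct comparison.** For one early donor-site score, d = 0.8 and power is 79%, with no dependence on ρ or k. For the mean of the 30-minute, 2-hour and 6-hour scores with equal pairwise correlation, the SD of the mean is √((1 + 2ρ)/3) = 0.816 at ρ = 0.5. If the effect is 0.8 SD at all three times, d = 0.8/0.816 = 0.98 and power is 92% (87–97% for ρ from 0.7 down to 0.3). If it is present at 30 minutes only, d = (0.8/3)/0.816 = 0.33 and power is about 20% (18–24%). The summary must therefore match the expected duration of effect.

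**The case against.** The strongest reply is that the sentence is merely badly worded. It never says within-patient. It sits beside phrases about the difference in the two groups, and the hydromorphone paragraph then announces the same test again for a plain between-group comparison. Study Design c) and f) describe pain in the same way. On that reading nothing is subtracted. This stands: the harmless reading is plausible, and the documents do not settle the matter.

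A reader might go further the other way and infer that the plan has committed to a change score and that lidocaine's effect will be subtracted out or reversed. The documents do not support that:

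- The own-control sentence is no evidence for it. It concerns narcotic use before surgery, not pain ratings.
- The pair of PACU arrival and 24 hours is a complete list only in the Group A text. Group B has three times; the Table of Events, Appendix A and the case report forms have four. Nothing names that pair as the analysed contrast.
- Full cancellation needs an equal effect at both times. An adverse-looking result needs a waning effect read as change over time. The order of subtraction is not given, and earlier minus later would flip the arithmetic sign. A growing effect is only diluted.
- For donor-site minus overall pain, power stays at 79% (at ρ = 0.5) if none of the relief spills over.

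The harmless reading does not rescue the plan. It requires setting aside the literal wording of the only sentence that specifies the pain test, and it still leaves scale and time unnamed.

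**Conclusion.** The point holds as a conflict within the plan and an unsuitable literal rule, not as proof that the trial will cancel or invert its result. The schedule facts are firm: no VNRS or chart pain score is planned before the lidocaine, so no difference of two scheduled ratings is a change from baseline or estimates the analgesic effect.

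If the sentence is followed literally, the 79% power of a direct early comparison is replaced by anything from a 5% rejection rate, when the effect lasts to 24 hours or is fully shared with overall pain, to 65–95% rejection in the adverse direction, when the effect has gone by 24 hours and the change over time is tested. These figures rest on an early effect of 0.8 SD, equal SDs, correlation 0.3 to 0.7 and the stated shares, none of which the documents supply. The wording should be settled before any comparison by arm, including the interim look.

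**What to change.** Replace the first sentence of the Analysis Plan with a direct between-group comparison of donor-site VNRS, using one pre-named time or summary already collected. Each patient's mean of the 30-minute, 2-hour and 6-hour scores is one option; a single named time or an area under the curve would also serve. Make 24-hour donor-site pain and overall pain secondary. State that one post-treatment rating is not subtracted from another. Because the case report forms allow for a patient who cannot give a score, say how a missing score enters the summary.

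Align the VNRS times in the Group A and Group B text with the Table of Events.

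Donor-site pain has no pre-operative value, since the wound does not yet exist. For overall pain, the last pre-operative chart score could be added as a covariate. That is optional in a randomised comparison and would extend the chart pull by one item.

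The cost is wording: no added visits, staff or patients. The downside is that one named summary may miss an effect confined to another time, so the choice should follow the expected duration of effect and be fixed before the data are compared by arm.

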- c) Consent will be obtained from non-intubated patients willing to participate in the study that are admitted to the Burn Service for treatment of their burn or wound. All patients will undergo general anesthesia. Standard induction will be performed with Fentanyl and Propofol. Maintenance will primarily be with the volatile agent sevoflurane. Acetaminophen 1g IV and Ketorolac 30mg IV will be administered for baseline pain control intraoperative within the last 30 minutes prior to extubation. Fentanyl, Hydromorphone or Morphine will be

titrated in at end of the case as part of standard management. Hydromorphone, as needed (PRN), orders will be written for pain control in the recovery room as well as one time dose of Oxycodone 5-15mg PO. If patient requires more than 2mg of Hydromorphone then subsequent pain will be treated with Ketamine IV (10mg every 15 minutes up to 50mg total) and 1-2mg of IV midazolam. If pain is still not adequately controlled patient will be treated with an additional 2mg of Hydromorphone IV and Hydromorphone PCA will be initiated. Once discharged from the PACU to the surgical floor the patient will have PRN Oxycodone PO every 4 hours and/or Hydromorphone PO every 4 hours in addition to PRN Hydromorphone 0.2-0.5mg available. If pain control is still not adequate patient will be started on Hydromorphone PCA. The amount of hydromorphone required in PACU and in the first 24 hours following surgery will be compared between the two groups as well as self-reported donor site and overall pain according to the Verbal Numerical Rating Scale (VNRS) obtained from the patient by Research staff and by the hospital staff per standard of care.

- d) Lidocaine 2% with Epinephrine 10 μ g/mL will be placed on the donor site immediately following harvesting until hemostasis has been obtained per the surgeon. The total of up to 7mg/kg, as recommended by leading anesthesia textbooks, of lidocaine solution will also be sprayed onto the patient's donor site based on patient's ideal weight (BMI 25 or actual patient's weight if BMI <25).¹⁰
- e) 50 patients split into two (study & control) groups.

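### The interim significance test at 10 per group has no boundary and no stated use; if either look can count at two-sided 0.05, type I error for one pain comparison is about 8.6–8.7%, not 5%

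*Combined protocol and SAP*

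**What the plan says.** All the relevant text is in section 6, Research Plan.

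- **Test.** The Analysis Plan compares pain ratings between groups with an independent-groups t-test, to "compare the mean rating between the difference of the two reported pain scale ratings". It does not say whether the test is one- or two-sided.
- **Level and power.** "An alpha level of 0.05 and power of 0.8 will be used to address the difference in the two groups". The same sentence appears again for hydromorphone. No other alpha is given.
- **Size.** "With an effect size (Cohen's d) of 0.8 it is estimated that 25 patients in each" group; the Study Design gives the matching total, "50 patients split into two (study & control) groups".
- **Interim.** The pain paragraph ends: "An interim analysis will be conducted at 10 patients in each group and significance will be analyzed". Nothing more is said about it.
- **Safety looks.** Safety Monitoring Plan item a reports one already done: "A safety analysis performed on our first 15 patients proved safety". Item f plans another: "After 10 additional evaluable patients, have been enrolled a second safety analysis will be performed; all investigators will be involved in data interpretation". Neither contains an efficacy rule or an alpha level.

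**The concern.** A significance test at 10 of 25 per group is a second chance to find p<0.05 on the same comparison. Testing twice at 0.05, with either result able to count, does not hold 5% overall. The plan would hold 5% if it set a stricter interim level with a matching final level, or if it said that the interim supports no claim. It does neither, so whether the interim counts could be decided after its p-value is known.

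Two things are at stake. A pain result reported as p<0.05 could carry a higher false-positive rate than stated. And an effect reported from 10 per group because it crossed 0.05 would be too large on average.

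**Working it through.** **Inputs.** From the Analysis Plan: alpha 0.05, power 0.80, d=0.8, 25 per group at the end, 10 per group at the interim. Assumed: two-sided tests, one pain comparison, and normal data with equal variances.

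**1. The plan's own sample size.** With n per group = 2(z_alpha + z_power)²/d²:

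- Two-sided: 2(1.960 + 0.842)²/0.64 = 24.5. The t-test version gives 25.5. Exact t-test power at 25 per group is 79.1%.
- One-sided: 2(1.645 + 0.842)²/0.64 = 19.3. The t-test version gives 20.03.

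The stated 25 fits a two-sided test, which is the reason for assuming one.

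**2. Type I error with two looks.** The information fraction is 10/25 = 0.40, so under the null the two test statistics have correlation √0.40 = 0.632.

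- Two-sided: P(|Z₁|>1.96 or |Z₂|>1.96) = 0.0863.
- One-sided 0.05 at both looks: 0.0832.

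Simulated t-tests at 10 and 25 per group (1,000,000 null trials) give 0.0866 two-sided and 0.0836 one-sided. A separate run of 4,000,000 null trials gives 0.0870 two-sided. In the first simulation the final test alone rejects in 0.0498, and 0.0368 are significant at the interim but not at the end. The excess is those interim-only results.

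**3. Size of early claims.** To reach p<0.05 at 10 per group, the difference must exceed t(0.975, 18 df) × √(2/10) = 0.94 observed SDs, which is already above the design value of 0.8. In 1,000,000 trials at a true d of 0.8, 39.5% cross. Their mean difference is 1.21 true SDs, and 1.21/0.8 ≈ 1.5. Only 3.8% of them show a difference below 0.8 true SDs.

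**4. Rules compared (two-sided).** Boundary pairs were solved for 5% overall by normal theory. Error and power are from the 1,000,000-trial simulations, with the normal-theory and larger-run values included in the first row's range. Early-claim chances under the two boundaries are exact.

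| Rule | Type I error | Power at d=0.8 | Chance of an early claim at d=0.8 |
|---|---|---|---|
| 0.05 at both looks, either counts | 8.6–8.7% | 81.1% | 39.5% |
| Final test only, 0.05 | 5.0% | 79.2% | none |
| 0.001, then 0.0496 | 5.0% | 79.1% | 4.0% |
| 0.0019, then 0.0492 (O'Brien-Fleming) | 5.0% | 79.0% | 6.1% |

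Equal levels at both looks would need to be 0.0283. If only the final test is used, exact power at 25 per group is 78.9% at 0.0492 and 71.4% at 0.0283.

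**5. Is the interim really the safety look?** The triggers differ. The interim needs 10 in each group, 20 patients in all. The first safety analysis used 15. The second comes after 10 more evaluable patients, about 25 in all. The interim sentence also sits in the pain-efficacy paragraph, directly after the sample size.

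**The case against.** The strongest reply is that the plan never says an interim result can count. It has no stopping rule and no early report, and it ties 25 per group to showing significance. Read that way, only the final test decides and the error is 5%. This stands as a possible reading, and it is why the 8.6–8.7% is conditional. It does not remove the defect: the text calls for significance to be assessed at the interim, 0.05 is the only level available, and nothing prevents the result from being claimed.

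Four smaller points have some force.

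- The exaggeration in step 3 matters only if interim data are reported or acted on. If enrolment continues and only the 25-per-group estimate is reported, it does not arise.
- The sample size is attributed to tables and Mead's resource equation, so inferring two-sided testing from it is not conclusive. Sidedness changes the result little.
- Safety Monitoring Plan item a suggests that lidocaine dosing may have changed after the first patients. The figures at d=0.8 assume one constant effect. The type I error does not depend on that assumption.
- Pain is rated at four times for both donor site and overall pain, and hydromorphone is tested too. The 8.6–8.7% covers one comparison and is not the trial-wide error rate.

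**Conclusion.** The concern holds and should be fixed before any efficacy result is reported. The omission is certain: a significance test is planned at 40% of the information with no boundary, no adjusted final level and no stated use. Its consequence is conditional. With one comparison, 0.05 at both looks and either able to count, type I error is 8.6–8.7% two-sided or 8.3–8.4% one-sided. It is 5% if the interim carries no claim. The plan's wording does not choose between these.

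**What to change.** Replace the interim sentence with one of these:

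- **(a)** *No between-group efficacy test will be done before the final analysis; interim review is limited to the safety analysis in Safety Monitoring Plan item f.*
- **(b)** *At 10 per group, efficacy on [one pain comparison, named in advance] may be claimed only if two-sided p<0.001; the final test at 25 per group uses two-sided p<0.0496.* Another pair that holds 5% overall, such as 0.0019 then 0.0492, would also serve.

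State the sidedness in either case.

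The documents do not say whether this interim has been run; they report only the 15-patient safety analysis, fewer than the 20 it needs. If it has been run, disclose that and claim efficacy only from the final analysis. If the interim could have counted, use a final level that allows for it: for example two-sided 0.0492, or 0.0283 if it is treated as an equal look. If it can be shown that the interim could never have counted, 0.05 remains valid and the lower level is only a precaution.

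**Cost.** One or two sentences. Options (a) and (b) need no extra patients and leave power at about 79%, against 81.1% if either look at 0.05 could count. The early claim is given up under (a) and becomes rare under (b), its chance at d=0.8 falling from 39.5% to 4.0%. If the interim has been run, a final level of 0.0492 costs almost nothing (78.9%). At 0.0283 power falls to 71.4%, and restoring 80% would take about 31 per group.

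### Pain and two hydromorphone comparisons each take the full 0.05, with no primary outcome and no success rule, so the trial-wide error rate is left open

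*Combined protocol and SAP*

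**What the plan says.** The Abstract (section 3) gives the aim as showing that topical lidocaine is effective in lowering both pain scores and narcotic requirements. Neither is ranked above the other.

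The Analysis Plan in section 6 has two paragraphs.

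- The first opens with pain: "An independent groups t-test (Student's t-test) will be performed to compare the mean rating between the difference of the two reported pain scale ratings". It then states "An alpha level of 0.05 and power of 0.8 will be used to address the difference in the two groups", and gives Cohen's d of 0.8, 25 patients per group and an interim look at 10 per group. It also contains a sentence on comparing each patient's narcotic use with use before surgery.
- The second covers narcotic use: "The amount of hydromorphone utilized in the PACU immediately post op and within the first 24 hours will be compared between the two groups". It continues "Once again, an independent groups t-test will be performed to compare the mean quantity of hydromorphone required between the two groups" and repeats the alpha and power sentence word for word, without an effect size or sample size of its own.

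Elsewhere in section 6, the second footnote to the Study Table of Events schedules the pain scores: "Performed at 30 minutes after extubation, 2 hours, 6 hours and 24 hours post-op for both donor site and overall pain". Study Design item f) says that narcotic use will be "analyzed per ideal body weight, per actual body weight in addition to donor site area".

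No section names a primary, secondary or co-primary outcome. None gives a testing order, a multiplicity adjustment, or a rule on which results must be significant for the aim to be met.

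**The concern.** A stated alpha of 0.05 and power of 0.8 describe a single decision. Here they are attached to at least three comparisons: pain, PACU hydromorphone and first-24-hour hydromorphone. How these combine into a conclusion about effectiveness is not stated. Under one plausible rule the false-positive rate for that conclusion exceeds 0.05. Under the other, power falls short of 0.8. Neither stated figure can be attached to the trial's conclusion until the rule is written.

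The pain variable adds to this. The plan analyses a difference between two ratings but does not say which two. They could be donor site and overall pain, two time points, or something else. Even if pain was meant to be primary, the comparison is not fixed before the data are seen.

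**Working it through.** **Inputs.** From the Analysis Plan: alpha 0.05 and power 0.8 (stated twice), d = 0.8, 25 per group, three comparisons. Not in the documents, so assumed: two-sided tests, and the correlations between outcomes, for which a range is shown.

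**Step 1: reproduce the sample size.**

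n per group = 2 × [(z(0.975) + z(0.80)) / d]² = 2 × [(1.960 + 0.842) / 0.8]² = 24.5, rounded up to 25.

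This matches the plan. The t distribution gives 25.5, so 26. A one-sided test would give 20, which does not match. Power at 25 per group is 0.807 (normal) or 0.791 (t). The sample size is therefore right for one two-sided test at the full 0.05.

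**Step 2: if any one of the three results may support the aim.** With no true effect:

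- independent tests: 1 − 0.95³ = 0.1426
- ceiling under any correlation (Bonferroni): 3 × 0.05 = 0.15
- correlated tests, by simulation:

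| Assumed correlations | Chance of at least one p < 0.05 |
|---|---|
| all 0.3 | 0.136 |
| all 0.5 | 0.125 |
| all 0.7 | 0.110 |
| all 0.9 | 0.084 |
| pain with hydromorphone 0.3, between windows 0.5 | 0.132 |
| pain with hydromorphone 0.5, between windows 0.7 | 0.120 |
| pain with hydromorphone 0.7, between windows 0.9 | 0.100 |

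The rows at 0.3 to 0.7 throughout use 400,000 draws of normal test statistics. The other rows use 100,000 runs of t-tests at 25 per group. The range is about 8-14%, above 0.05 throughout.

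**Step 3: if pain and narcotic use must both succeed.** With one hydromorphone window fixed in advance, or both required, a false joint claim needs a significant result on at least one outcome with no true effect. Its probability is therefore at most 0.05. Joint power is lower than single-test power. Taking d = 0.8 for every outcome (an assumption, since the plan gives no effect size for hydromorphone) and the normal figure of 0.807:

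- two independent outcomes: 0.807² = 0.651
- three independent outcomes: 0.807³ = 0.526
- perfect correlation: 0.807

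Positive correlation short of 1 falls between these limits.

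**Step 4: cost of splitting alpha instead.** Bonferroni over three tests uses 0.05 / 3 = 0.0167. This needs 33 per group (normal) or 35 (t), that is 66 or 70 patients in total. Keeping 25 per group leaves power of 0.668 or 0.637 per test.

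**Not counted above.** The schedule yields 4 times × 2 scales = 8 pain scores, and narcotic use is scaled three ways. The interim look is a separate source of inflation: a single outcome tested at 0.05 at both 10 and 25 per group has an error rate of about 0.088.

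**The case against.** The strongest reply is that the any-one-result rule comes from the reader and not from the plan. That stands. No section says that one significant test is enough. The aim joins pain and narcotic use with a conjunction, and each test taken alone has level 0.05 at a single final analysis. A reader might infer that the stated alpha is simply wrong. The documents support less: no success rule is given, so whether 0.05 holds for the conclusion depends on a choice not yet made. Nor does the conjunctive reading rescue the plan, because no such rule is written and the stated power would then not apply.

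It can also be said that the trial was sized on pain, since d and 25 per group stand in the pain paragraph and the hydromorphone paragraph has neither. This is the natural reading. But the same paragraph also brings in narcotic use, the plan never calls pain primary, and hydromorphone receives the same alpha and power.

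A reader might count every pain score and every scaling as a separate test and arrive at ten or fourteen tests, with much larger error rates. The Analysis Plan does not support that count. The table footnote is an assessment schedule, and item f) states no test or alpha for each scaling. Scalings of one opioid total would also be highly correlated. These items show room for choice, not a stated set of tests at 0.05.

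Finally, the Background presents the trial as further support for the treatment and a step towards later work, which softens the consequences of a false positive. Against that, the Abstract sets out to demonstrate effectiveness, and the plan states an alpha and a power.

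**Conclusion.** The point holds in a conditional form. Three comparisons are each given alpha 0.05 and power 0.8, with no primary outcome, no order and no success rule, and the pain variable is undefined.

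If any one significant result may support the aim, the false-positive rate over these three tests is about 8-14%, with a ceiling of 15%. This assumes pairwise correlations from 0.9 down to 0.3, which the documents do not give, and excludes the interim look. PACU use may form part of the 24-hour total, so the lower end is plausible. If pain and narcotic use must both succeed, the error stays within 0.05, but joint power falls below the stated 0.8 unless the outcomes are essentially perfectly correlated.

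The sample size arithmetic is not at fault: 25 per group is right for one two-sided test. What is missing is the statement of which test that is.

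**What to change.** Amend the Analysis Plan before any outcomes by arm are seen:

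1. Name one primary comparison to which alpha 0.05, power 0.8 and 25 per group apply. Donor-site VNRS at one scheduled time would serve. State that it replaces the undefined difference of two ratings.
2. Test first-24-hour hydromorphone at 0.05 only if the primary is significant.
3. Report PACU hydromorphone, overall pain, the other times and the scalings as estimates with 95% confidence intervals and no significance claim.

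This takes a few sentences, keeps 50 patients, and leaves the full alpha on the primary comparison. The price is that a narcotic-use claim can be made only if the primary succeeds. Requiring both outcomes, or splitting alpha, would also be valid, at the cost in power or patients shown in the working.

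Timing matters. The Safety Monitoring Plan says that lidocaine levels in the first 15 patients have been reviewed, and such levels can indicate allocation. A second safety analysis involving all investigators and an interim look at 10 per group are also planned. The amendment should record that pain and narcotic data by arm had not been seen when the primary was chosen. The interim look needs its own rule, since the fixed order holds 0.05 only for the final analysis.
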